8.3.2 Negative Pressure Wound Therapy (NPWT)

NPWT has very few complications associated with its use. There are few reports of fistula development with the use of NPWT but these are in patients where the NPWT has been placed directly over intestines and not on a closed incision. Additionally, NPWT is widely used in treatment of an open wound, and placed directly over the fascia with few reported complications. When large amounts of fluid are removed from an incision large fluid losses can lead to hemodynamic changes in patients; however, it is anticipated that this fluid loss would be much greater in an open wound (NPWT is placed directly over the fascia and within the subcutaneous tissue) than over a closed wound. Fluid status will be followed closely and managed per the standard postoperative protocol.

There are also some less serious complications such as local cutaneous reactions (rash, redness, pruritis, urticaria), allergic reaction, maceration, minor soft tissue damage, skin stripping, minor bleeding, pain, bruising. All patients will be monitored closely for signs of skin irritation and will be treated appropriately with barrier creams as needed. In cases where NPWT is used to aid in healing by secondary intention, the NPWT is in place for weeks to months with minimal skin irritation; it is anticipated that this risk of irritation will be even lower when the NPWT device is in place for only 2-3 days.

There are some other uncommon risks associated with the NPWT including,

bleeding complications (associated with the surgical procedure, concomitant therapies and co- -morbidity), first degree burn (if device gets warm), exposure related infection, localized infection, physical discomfort, minor desiccation (due to dressing leak), moderate soft tissue damage (i.e. due to trip hazard, tubing entanglement) and deterioration of the wound (due to lack of visibility of incision site through dressing).

8.3.3 All Patients, Regardless of Post-Operative Care

There is a small risk of loss of confidentiality; however steps will be taken to minimize this by assigning the patient a unique patient identifier at the time of study enrollment to be used in place of direct identifiers. A master list will be kept in OnCore, the Cancer Center's password protected clinical database that resides on the University of Minnesota server.

8.4 Supportive Care

Optimal patient care will be given to all patients regardless of their post-operative wound care assignment per institutional guidelines, including those for infection control.

8.5 Duration of Study Participation

It is expected the duration of study participation will be less than 2 months.

All patients will be assessed for wound complications (including infection, dehiscence and evisceration) at their 1st post-operative visit approximately 10-14 days after surgery.

Patients will continue to be tracked for wound complications for a minimum of 4 weeks after surgery by review of clinic notes/medical records. For patients who develop a wound complication, the type of complication, treatment received and outcomes will be captured.

For patients with a cancer diagnosis that requires anti-cancer therapy (chemotherapy and/or radiation), the therapy start date of therapy will be recorded.

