Most gynecologic and many intra-abdominal malignancies are treated with an initial surgical procedure. Over the past 20 years there has been a dramatic increase in obesity rates in the US with more than one third (35.7%) of US adults being obese ($BMI > 30\text{kg}/\text{m}^2$) or morbidly obese ($BMI > 35\text{ kg}/\text{m}^2$). There is a direct link between obesity and wound complications following surgery with an increasing BMI leading to increasing rates of complications. Negative pressure wound therapy (NPWT) is a system that utilizes sub-atmospheric pressure to improve wound healing by increasing the formation of granulation tissue. NPWT has been shown to improve outcomes in both the orthopedic and cardiothoracic surgery populations. To date, there is no prospective study evaluating the application of prophylactic NPWT in laparotomy patients.

Primary Objective:

To evaluate the rate of wound complications with negative pressure wound therapy (NPWT) as compared to standard surgical closure and post-operative wound care in obese patients ($BMI \geq 35\text{ kg}/\text{m}^2$) undergoing laparotomy for a suspected gynecologic malignancy or other abdominal cancer.

Secondary Objective:

To compare the time between surgery and the start of anti-cancer therapy (chemotherapy and/or radiation therapy) between those patients diagnosed with a malignancy who received NPWT and those who received standard surgical closure

Patient Population:

Morbidly obese ($BMI \geq 35\text{ kg}/\text{m}^2$) adult patients presenting for surgical treatment of a known or suspected gynecologic malignancy or other abdominal cancer by laparotomy incision

Study Procedures:

After screening and obtaining written consent, but prior to surgery 1:1 randomize to either:

- Negative pressure wound therapy (NPWT)
- Standard surgical closure

Assess wound complications at 1st post-operative visit (10-14 days after initial procedure)

If no cancer diagnosis, final study assessment at 1st post-operative visit

If cancer diagnosis is made, chart review at 3 months post-surgery to determine time between surgery and start of anti-cancer therapy (chemotherapy and/or radiation therapy)

Enrollment Goal:

200 patients randomized over 24 months

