2.0 Study Objectives

The primary goal of this study is to evaluate if the use of prophylactic negative pressure wound therapy (NPWT) over a closed incision improves postoperative outcomes and cancer care for morbidly obese (BMI ≥ 35 kg/m²) patients undergoing laparotomy for treatment of a suspected gynecologic or other abdominal malignancy is comparable or better to wound healing after standard surgical closure and wound care.

This comparison will be achieved by:

- Assessing the incidence of wound complications, specifically, dehiscence and infection at the 1st post-operative visit (10-14 days after surgery)
- documenting the time from surgery to the start of anti-cancer treatment in a subset of patients receiving a cancer diagnosis by chart review approximately 3 months after surgery

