10.0 Statistical Considerations

10.1 Data Analysis

The patient population demographics will be descriptively summarized both combined and by treatment randomization. All analyses will be conducted under the intention-to-treat principle and all deviations and adverse events will be reported.

Our primary aim is to compare rate of wound complications (wound dehiscence or infection) identified within first month after surgery by treatment group (standard of care or NPWT). As this is a large randomized trial, the comparison will first be made using a Chi-squared test as we anticipate approximate balance in all measured and unmeasured confounders. These results will be supplemented using logistic regression, including demographics and clinical variables (including surgeon) as appropriate.

Our secondary aim is compare the time from surgery to starting adjuvant therapy among those with confirmed malignancies. This will be measured in days and will be available regardless if patients undergo treatment at our study facilities as their surgeon will manage their care and maintain contact up to 6 months regardless of follow-up location. The effect of NPWT on the length of the number of days until treatment will be assessed using Poisson regression, adjusting for over-dispersion if necessary. As stated above, we will supplement these results adjusting for demographic and clinical variables as appropriate.

For all analyses, p-values of less than 0.05 will be considered statistically significant and will be performed using SAS software version 9.3 (Cary, NC).

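### Section 8.5 expects participation of under 2 months and sets no time for collecting the therapy start date, although the secondary endpoint is read at a chart review about 3 months after surgery

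*Combined protocol and SAP*

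**What the plan says.** Section 8.5, on duration, says: "It is expected the duration of study participation will be less than 2 months". It then gives a time for the first post-operative visit (about 10 to 14 days) and for wound tracking from the records (at least 4 weeks). For patients whose cancer requires chemotherapy or radiation it says only that "the therapy start date of therapy will be recorded", with no time attached.

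The synopsis, under Study Procedures, sets the reading time: "If cancer diagnosis is made, chart review at 3 months post-surgery to determine time between surgery and start of anti-cancer therapy". Section 2.0 repeats it: the time to treatment is documented "in a subset of patients receiving a cancer diagnosis by chart review approximately 3 months after surgery".

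Section 10.1 says the number of days will be available wherever the patient is treated, because "their surgeon will manage their care and maintain contact up to 6 months regardless of follow-up location". It plans Poisson regression on the days and gives no rule for a patient who has not started therapy when the chart is read. Section 10.2 expects about 70% of patients to have a malignancy (140 for this analysis), expects control-arm therapy to start 4 to 6 weeks after surgery, and calls the secondary aim descriptive.

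**The concern.** Section 8.5 is where Section 8 sets out how long patients are followed, yet its stated duration ends before the review that measures the secondary endpoint, and it does not mention that review. For most of the trial population the two statements cannot both describe follow-up.

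The horizon matters because of what the endpoint is meant to show. The rationale in Sections 1.0 and 3.0 is that wound complications delay adjuvant therapy. Late starts are therefore the signal, and on the assumed complication rates (25% control, 10% NPWT) they should be more frequent in the control arm. If collection did stop at about 2 months, starts would be lost unequally by arm and the observed difference would be pulled toward zero. A cut-off at 3 months has the same effect on a smaller scale, because the plan does not say how patients not yet started enter the analysis.

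**Working it through.** **Step 1. The plan's own figure.** 0.70 × 200 = 140 patients with a malignancy, or 70 per arm. This matches Section 10.2.

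**Step 2. The horizons side by side.**

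| Place | What it fixes | Time after surgery |
|---|---|---|
| Section 8.5 | Expected participation | under 2 months (about day 60) |
| Section 8.5 | Therapy start date | none given |
| Synopsis; Section 2.0 | Chart review for therapy start | about 3 months (day 91) |
| Section 10.1 | Surgeon contact | up to 6 months (day 182) |
| Section 10.1 | Primary endpoint | first month |

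The first and third rows conflict by about one month. The 6-month contact explains why dates can be obtained; it is not a reading time and fits a 3-month review. The primary endpoint lies inside every horizon.

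**Step 3. Who would be affected.** Expected control starts are days 28 to 42. To pass day 60, a start must slip 60 − 42 = 18 to 60 − 28 = 32 days beyond that. Typical starts are safe; only delayed ones are exposed.

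**Step 4. Size if a cut-off were applied literally.** The documents give neither a standard deviation nor a delay size, so both are assumed, and two models are shown. Let p be the complication share (0.25 control, 0.10 NPWT). For patients without (0) and with (1) a complication, let F = P(T ≤ t) and E = the mean of T counted only where T ≤ t. The arm mean among starts seen by day t is

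[(1 − p)E₀ + pE₁] / [(1 − p)F₀ + pF₁].

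*Model A*: normal; mean 35 days, SD 7 without a complication; mean 56 (SD 18), 63 (SD 20) or 70 (SD 20) with one. Worked case, mean 63 and t = 61:
- F₀ = 0.9999, E₀ = 34.99; F₁ = Φ(−0.1) = 0.4602, E₁ = 63 × 0.4602 − 20 × 0.3970 = 21.05.
- Control: (0.75 × 34.99 + 0.25 × 21.05) / (0.75 × 0.9999 + 0.25 × 0.4602) = 31.51 / 0.8650 = 36.43.
- NPWT: (0.90 × 34.99 + 0.10 × 21.05) / (0.90 × 0.9999 + 0.10 × 0.4602) = 33.60 / 0.9459 = 35.52.
- Observed difference 0.91 days; true difference 0.15 × (63 − 35) = 4.20 days.

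*Model B*: lognormal; mean 35, SD 14 without a complication; a complication adds 14, 21 or 28 days (same SD). The true difference is 0.15 × the delay.

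| Model | True difference (days) | 2-month stop | Shrinkage | Day-91 stop | Shrinkage |
|---|---|---|---|---|---|
| A, mean 56 | 3.15 | 1.02 | 68% | 2.93 | 7% |
| A, mean 63 | 4.20 | 0.91 | 78% | 3.51 | 16% |
| A, mean 70 | 5.25 | 0.81 | 85% | 3.99 | 24% |
| B, +14 days | 2.10 | 1.47 | 30% | 2.06 | 2% |
| B, +21 days | 3.15 | 1.76 | 44% | 3.04 | 4% |
| B, +28 days | 4.20 | 1.61 | 62% | 3.94 | 6% |

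The 2-month stop is day 61 in model A and day 60 in model B. In model A it loses about 7 to 12 control and 3 to 5 NPWT starts per 70. In model B it loses 9% to 18% of control and 7% to 10% of NPWT starts.

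**The case against.** A reader might infer that the plan discards therapy starts after 2 months. The documents do not support that. Section 8.5 states an expectation, records the start date without a limit, and describes no close-out of patients at 2 months. The synopsis and Section 2.0 both specify the later review. Participation could also mean visits and wound follow-up only, with the review done afterwards from charts. That reading is possible, but Section 8.5 does not favour it: under the same heading it lists wound tracking from records and recording of the therapy date, so it treats chart-based collection as part of participation. The wording still needs reconciling.

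A reader might also count the 6 months in Section 10.1 as a third, competing horizon. It is not one.

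The size depends on the model, and that criticism stands. In model A almost no uncomplicated patient starts after day 61, so the late starts come from complications by construction. In model B 5.6% of uncomplicated patients start after day 60. With a 14-day delay they make up 0.90 × 0.0557 / 0.0696 = 72% of late NPWT starts, and the shrinkage is only 30%. The counts per 70 are also upper figures, because Section 8.5 limits the start date to cancers that require therapy and not every malignancy will.

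The stakes are limited: Section 10.2 calls the secondary aim descriptive. A descriptive estimate is still biased by arm-unequal loss, but no confirmatory claim depends on it.

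**Conclusion.** The inconsistency stands as a matter of text. The under-2-month duration in Section 8.5 does not accommodate the 3-month review in the synopsis and Section 2.0, and Section 8.5 gives no time for collecting the date that the review is meant to supply. It concerns about 70% of patients by the plan's figure.

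Loss of delayed starts is a conditional risk, arising only if Section 8.5 is applied literally. The shrinkage figures rest on assumed delays and spreads, on complication rates of 25% and 10%, and on dropping late starters from the analysis. They show that the choice of horizon can matter; they do not estimate a bias in this trial. The residual shrinkage at 3 months is a separate reason to say how patients not yet started are handled. Sample size and the primary analysis do not change. Severity: minor to moderate.

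**What to change.** In Section 8.5, replace the under-2-month statement with two parts:

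- All patients: wound tracking for a minimum of 4 weeks, as now.
- Patients with a cancer diagnosis: a chart review at 3 months that records the therapy start date or that therapy has not started. Where none has started, one further chart check within the 6-month surgeon contact that Section 10.1 already relies on.

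In Section 10.1, state that patients still not started are censored at their last review and not dropped. Ordinary Poisson regression on days cannot hold censored values, so the analysis needs a method that can, such as Kaplan-Meier estimates by arm with a regression model that allows censoring. The chart form should mark patients whose cancer requires no further therapy separately, so that they are not counted as waiting.

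Use the same wording in the synopsis and Section 2.0. The consent pages are not in the review copy; if they state a duration, it should match.

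The cost is a wording amendment, a longer stated participation, and one extra chart check for a few patients. On the day-91 figures that is at most 2.6 control plus 1.0 NPWT, or about 4 of 140, in model A. No visit, treatment or sample size changes.

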9.0 Prevena™ Incision Management System¹⁴

The Prevena Incision Management System will be provided by Kinetic Concepts Inc. (KCI) for the purposes of this study.

9.1 Indication for Use

The Prevena Incision Management System is intended to manage the environment of surgical incisions that continue to drain following suturing or stapling by maintaining a closed environment and removing exudate by negative pressure

wound therapy. This study intends to use the device according to its approved indications.

9.2 Optimum Use Conditions

For maximum benefit is should be applied immediately post-surgery and used continuously for a minimum of two days and up to a maximum of seven days. For the purposes of this study the device will be used for two to three days with removal prior to discharge from the hospital.

9.3 Contraindications

Sensitivity to silver – potential participants of this study with a history of this sensitivity will be excluded per section 6.6.

9.4 Warnings – refer to the Clinician Guide for full details

<http://www.kci1.com/cs/Satellite?c=Page&childpagename=KCI1%2FKCILayout&cid=1229636259704&pagename=KCI1Wrapper>

- Bleeding – before applying, ensure that hemostasis has been achieved and tissue planes have been approximated. If active bleeding develops or frank blood is seen in the tubing or canister leave the Dressing place, but turn off the device and provide immediate medical assistance.
- Infected wounds – monitor the wound, peri-wound area, exudate, and patient's general clinical status for signs of infection; if infection develops Prevena Therapy should be discontinued
- Allergic response – the Prevena Incision Dressing has an acrylic adhesive coating and a skin interface layer lined with silver which may present a risk of an adverse reaction in patients with known hypersensitivity. Patients with a known silver or tape sensitivity are not eligible for this study.
- Defibrillation – remove the Prevena Incision Dressing if defibrillation is required in the area of the dressing placement
- Magnetic Resonance Imaging (MRI) – the Prevena Therapy Unit is unsafe in the MRI environment and interruption of therapy during an MRI may reduce its effectiveness. The Dressing can typically stay in place during the MRI.
- Other diagnostic imaging - the Prevena Incision Dressing contains metallic silver which may impair visualization with certain imaging modalities.
- Hyperbaric Oxygen Therapy – do not take the Prevena Therapy Unit or the Prevena Incision Dressing into the chamber
- Canister full – if any time the canister becomes full of fluid as indicated by the Maximum Capacity Alert or visual inspection, turn off the therapy unit and attend to the canister.

Refer to the Prevena Incision Management System website with links to the Clinician Guide for complete device details.
<http://www.kci1.com/KCI1/prevena#>

10.0 Statistical Considerations

10.1 Data Analysis

The patient population demographics will be descriptively summarized both combined and by treatment randomization. All analyses will be conducted under the intention-to-treat principle and all deviations and adverse events will be reported.

Our primary aim is to compare rate of wound complications (wound dehiscence or infection) identified within first month after surgery by treatment group (standard of care or NPWT). As this is a large randomized trial, the comparison will first be made using a Chi-squared test as we anticipate approximate balance in all measured and unmeasured confounders. These results will be supplemented using logistic regression, including demographics and clinical variables (including surgeon) as appropriate.

Our secondary aim is compare the time from surgery to starting adjuvant therapy among those with confirmed malignancies. This will be measured in days and will be available regardless if patients undergo treatment at our study facilities as their surgeon will manage their care and maintain contact up to 6 months regardless of follow-up location. The effect of NPWT on the length of the number of days until treatment will be assessed using Poisson regression, adjusting for over-dispersion if necessary. As stated above, we will supplement these results adjusting for demographic and clinical variables as appropriate.

For all analyses, p-values of less than 0.05 will be considered statistically significant and will be performed using SAS software version 9.3 (Cary, NC).

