1.0 Introduction and Overview

Up to 90% of type I (estrogen-dependent) endometrial cancer patients are obese¹ and obesity is considered a risk factor for both endometrial and ovarian cancers². Most gynecologic malignancies are treated with an initial surgical procedure. A number of colorectal diseases are also increased with obesity including diverticular disease and colorectal cancer^{15,16, 17}. A central challenge for surgeons is the increase in the rates of wound complications following surgery given the rise in obesity. The rate of wound complications for gynecologic oncology procedures is 34% overall and is highly correlated with BMI⁴. Patients with a BMI of ≥ 40 kg/m² had a 10 fold increase in the risk of wound complications compared to normal weighted patients⁶. Some patients are able to circumvent this problem with a minimally invasive approach to their surgery; however, obesity increases the risk of conversion to an open procedure. Wound complications are not only distressing to patients but can also delay necessary adjuvant therapy such as chemotherapy and radiation.

Negative pressure wound therapy (NPWT) is a system that utilizes sub-atmospheric pressure to improve wound healing by increasing the formation of granulation tissue. The mechanism for this improved wound healing is thought to be increased local blood flow, mechanical stress at the wound surface, removal of factors that inhibit wound healing and decreased bacterial burden. To date there are good data to show the benefit of using NPWT to treat wound complications that arise post-operatively. In the orthopedic and cardiothoracic surgery literature there is evidence to suggest that prophylactic NPWT placed over a closed incision decreases wound dehiscence and infection rate, with a 40% decrease in orthopedic patients and 4-fold decrease in morbidly obese cardiothoracic patients. However, to date, there is no prospective study evaluating the application of prophylactic NPWT in laparotomy patients.

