3.0 Background and Significance

The obesity epidemic is a growing problem in the US and its effects are felt very heavily on the gynecologic oncology population. Both endometrial and ovarian cancers are increased in the obese populations^{1,2}, and the majority of gynecologic malignancies are initially treated with a surgical procedure. A number of colorectal diseases are also increased with obesity including diverticular disease and colorectal cancer^{15,16, 17}. Risks and complications of surgery are much greater in the obese population. The reported rate of wound complications in the gynecologic oncology population is 34-40% depending on the location⁴. Wound complications are highly correlated with patient BMI. These wound complications can lead to a delay in necessary adjuvant therapies such as chemotherapy and radiation. It is known that delays in the initiation of adjuvant therapy can have a negative impact on survival.

NPWT is a system that uses sub-atmospheric pressure to alter the physiologic and chemical environment of the wound bed. It is postulated that this works through several different mechanisms including increased local blood flow, increased mechanical stress leading to increases in cellular proliferation, more effective removal of factors that inhibit wound healing including bacteria and fluid^{7,8}. Studies using NPWT in an open laparotomy incision to facilitate healing by secondary intention show that it leads to decreased wound healing time¹⁰. However, to date, there are few studies evaluating the use of prophylactic NPWT over a closed incision, and most of the existing data is in the orthopedic and cardiothoracic surgery literature. The use of prophylactic NPWT over orthopedic wounds has been shown to decrease wound dehiscence and infection rates by 40%, and has decreased the rate of wound complications 4-fold in obese patients undergoing cardiothoracic surgery^{12,13}. However, it is unclear if this same benefit will be seen with abdominal laparotomy incisions.

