4.0 Wound Complications at the University Of Minnesota

We performed a retrospective chart review of all patients with a $BMI \geq 30 \text{ kg/m}^2$ who have undergone a laparotomy for a known or suspected gynecologic malignancy at our institution in the past 6 months. We found that of 51 obese patients to undergo a laparotomy, 13 (25%) had some form of wound complication, either a wound dehiscence or infection. This is on par with what is reported in the literature. Further, 5 of the 51 patients were readmitted to the University of Minnesota hospital due to their wound complications, for a readmission rate of almost 10%. The results of this chart review were used to inform our sample size calculations.

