6.0 Patient Selection

Study entry is open to adult patients regardless of gender, race or ethnic background. While there will be every effort to seek out and include minority patients, the patient population is expected to mirror the obese patient population at the University Of Minnesota.

Inclusion Criteria

- 6.1 Known or suspected gynecologic or other abdominal malignancy (such as colorectal, liver, pancreatic, kidney and stomach) for which laparotomy is planned
- 6.2 Obese – defined as a Body Mass Index (BMI) ≥ 35 kg/m² as calculated in the Epic computer record
- 6.3 18 years of age or older
- 6.4 Able and willing to provide written consent

Exclusion Criteria

- 6.5 Known true tape allergy
- 6.6 Sensitivity to silver
- 6.7 History of intolerance to Negative Pressure Wound Therapy

[figure not shown]

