7.0 Patient Registration and Randomization

Patients will be registered into OnCore after written consent is provided and eligibility is confirmed (appendix I), but prior to the performance of any research related procedures.

Randomization will occur at the time of registration. To prevent bias and minimize the possibility of confounding, consenting patients will be randomly assigned 1:1 to either NPWT or standard of care.

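### The primary chi-squared test is valid but makes no use of BMI, which the protocol itself calls a strong correlate of the outcome; adjusting for it costs little, for a gain the documents cannot size

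*Combined protocol and SAP*

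**What the plan says.** Section 10.1 (Data Analysis) compares the proportion of patients with dehiscence or infection in the first month between arms. It states that "the comparison will first be made using a Chi-squared test as we anticipate approximate balance in all measured and unmeasured confounders". A logistic regression then supplements this. Surgeon is the only covariate named for it, and the choice of the rest is left open.

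Section 10.2 (Sample Size Calculations) assumes 25% versus 10%, a two-sided Z-test at 0.05 and 80% power. It arrives at 97 per arm, rounded up to 100.

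On BMI, section 3.0 (Background and Significance) says: "Wound complications are highly correlated with patient BMI". Section 1.0 (Introduction and Overview) adds that patients with a BMI of 40 or more "had a 10 fold increase in the risk of wound complications compared to normal weighted patients".

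On timing, section 6.0 (Patient Selection) requires a BMI of at least 35 kg/m² "as calculated in the Epic computer record". Section 7.0 says "Patients will be registered into OnCore after written consent is provided and eligibility is confirmed", and then "Randomization will occur at the time of registration". It describes 1:1 assignment and mentions no stratification by BMI.

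**The concern.** The reason given for the unadjusted test is expected balance of confounders. That answers whether the comparison is unbiased. It does not answer whether the comparison is as precise as it could be. A baseline variable that predicts the outcome adds variation to each arm's complication rate even when the arms are perfectly balanced on it, and an unadjusted test leaves that variation in the error term.

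The protocol names such a variable, and its value is fixed before assignment for every patient. Neither the randomization as described nor the primary test uses it. Planned power is only about 80%, so a few points from information already on record could be worth having.

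**Working it through.** **1. Reproduce the plan's figure.** The inputs are those of section 10.2. With unpooled variance,

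n = (1.960 + 0.842)² × (0.25×0.75 + 0.10×0.90) / 0.15² = 96.8, so 97 per arm.

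Power = Φ(0.15 / √(0.2775/n) − 1.960). This gives 80.1% at 97 per arm and 81.3% at 100. With pooled variance the figures are 79.0% and 80.2%. The plan's 97 stands.

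**2. What has to be assumed.** The documents give neither the association between BMI and complications within BMI 35 and above nor the distribution of BMI in that range. Both were therefore varied. The outcome model was logit P(complication) = a(arm) + β × (BMI in SD units), with β = log(odds ratio per SD). The intercepts were set so that the marginal rates stayed at 25% and 10%, with 100 patients per arm. Two BMI shapes were used:

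- normal, 10,000 simulated trials per row;
- right-skewed, BMI = 35 + gamma with mean 7 and SD 6, 60,000 simulated trials per row.

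**3. Power of the chi-squared test and of the BMI-adjusted standardised risk difference (RD).** Power is in % and gain in points.

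| Assumed odds ratio per SD | Normal: chi-squared | Normal: adjusted RD | Gain | Skewed: chi-squared | Skewed: adjusted RD | Gain |
|---|---|---|---|---|---|---|
| 1.0 | 81.9 | 81.9 | 0.0 | 82.0 | 82.0 | 0.0 |
| 1.25 | 81.2 | 81.5 | +0.3 | 81.6 | 81.8 | +0.2 |
| 1.5 | 81.8 | 82.5 | +0.7 | 81.7 | 82.9 | +1.2 |
| 1.75 | 82.0 | 83.4 | +1.4 | 81.7 | 83.9 | +2.2 |
| 2.0 | 81.7 | 84.1 | +2.4 | 81.8 | 85.4 | +3.6 |

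The Monte Carlo standard error of the skewed-case gains is 0.04 to 0.11 points. It is larger in the normal case, which used fewer trials. A more strongly skewed (exponential) BMI gave +3.8 at an odds ratio of 2.0.

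**4. Choice of test.** The adjusted likelihood-ratio test agrees with the RD test to within 0.1 point in every row. The adjusted Wald test is 1.0 to 1.3 points lower throughout, so with no BMI association it loses about 1 point against chi-squared.

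**5. Hand check.** In the skewed case the ratio of unadjusted to adjusted RD variance was 1.024 at an odds ratio of 1.5 and 1.090 at 2.0. In the unpooled formula at 100 per arm, 0.15/√0.002775 = 2.8475.

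- Odds ratio 1.5: Φ(2.8475 × √1.024 − 1.960) = 82.2%, which is +0.9 over 81.3%.
- Odds ratio 2.0: Φ(2.8475 × √1.090 − 1.960) = 84.4%, which is about +3.2.

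These are close to the simulated gains. In patients, 200 × 1.024 ≈ 205 and 200 × 1.090 = 218, so the adjustment is worth roughly 5 to 18 extra patients under those assumptions.

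**6. Type I error.** With normal BMI and 25% in both arms, chi-squared gave 4.4–4.8%, and the adjusted RD and likelihood-ratio tests 4.7–5.2%. With skewed BMI and 17.5% in both arms, the figures were 5.1–5.2% for chi-squared, 5.2–5.3% for RD and 5.3% for likelihood-ratio. No test departs materially from 5%.

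**The case against.** The strongest reply is that nothing here is wrong. The chi-squared test is valid under randomization, agrees with the Z-test used for sample size, and targets the same 15-point difference. An unadjusted primary test with an adjusted supplement is a legitimate design. All of that stands, and it is why the point is optional.

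Second, a reader might infer that the plan ignores BMI altogether. The documents do not support that: the supplementary regression is broad enough to include it. But that model is not the one on which the primary conclusion rests, so its possible use of BMI does not restore precision to the primary test.

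Third, a reader might take the 10-fold figure as proof of a large gain. It compares BMI of 40 or more with normal weight, and the trial enrols nobody of normal weight. It does not measure the gradient among patients at 35 and above, which could be weak. At an odds ratio of 1.5 or less, the gain is no larger than the step from 97 to 100 per arm (80.1% to 81.3%, or 1.2 points).

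Fourth, surgeon is the only covariate the protocol names, so why BMI? Because BMI is the baseline variable for which the protocol itself asserts a strong association, and it enters as a single term. The planned rates imply only 100×0.25 + 100×0.10 = 35 events, which limits how many terms a primary model should carry. The number of surgeons is not given.

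Finally, the checklist in Appendix I records BMI only as Yes or No against the threshold. It should not be assumed that the numeric value is already in the study data.

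**Conclusion.** The point holds as an efficiency option. The justification in section 10.1 covers validity but not precision, and the primary test does not use a variable that the protocol calls highly correlated with the outcome and that is known before randomization.

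The size of the gain is unknown. Under assumed odds ratios per SD of 1.0 to 2.0, it is about 0 to +2 points with normal BMI and 0 to +4 with right-skewed BMI, from a base of about 82%. The upper end needs both skew and a fairly steep gradient, neither of which the documents establish. Stopping at 2.0 is itself a choice: at 2.5 the simulated gains are about +4 (normal) and +6 (exponential). With the RD or likelihood-ratio test there is essentially no loss if BMI is not prognostic.

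The results do not support reading the chi-squared test as invalid or the trial as underpowered for want of adjustment. Whether 25% is the right control rate is a separate sample-size question and plays no part here.

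**What to change.** Before outcome data are seen, amend section 10.1 so that the primary comparison is a logistic model with treatment and continuous BMI. State the functional form of BMI in advance. Report a standardised risk difference with its 95% CI, which keeps the 15-point contrast used for planning (an adjusted odds ratio would not). Take the p-value from the risk difference or from a likelihood-ratio test, not from the Wald test. Keep the chi-squared test as a supportive analysis.

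The cost is a short change to the SAP, a little code, and copying each patient's numeric BMI from the Epic record into the study data. The downsides are a slightly more complex primary analysis, some dependence on the chosen form for BMI, and no gain if BMI is not prognostic at 35 and above.
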